### **Cohort B: Panoramic Bracelet Device**

This section contains a list of digital endpoints related to the study primary objective in Cohort B: i.e. *Evaluate the Panoramic Bracelet device and associated algorithms in the quantification of physical activity (eg sleep), scratch, and wear time, as compared to another accelerometry device (GENEActiv) during the at-home period.*

*The position of the GENEActiv device and the Panoramic Bracelet device closeness to the wrist (i.e., proximity of the device) will be balanced per age group. Approximately half the participants in each age group will wear the Panoramic Bracelet device proximal to the wrist and the GENEActiv device more distal to the wrist and vice versa*

#### **3.1.2. Sleep, Scratch and Wear Time**

Each variable will be summarized daily or nightly, as appropriate.

##### **3.1.2.1. Sleep Parameters**

- Total sleep opportunity (min)
- Total sleep time (min)
- Percent time asleep (%)
- Number of wake bouts (no.)
- Sleep onset latency (min)
- Wake after sleep onset (min)

The sleep-related parameters for GeneActive and Panoramic Bracelet will be derived by the SleepPy algorithm.

##### **3.1.2.2. Scratch Parameters**

- Total scratch duration (min.)
- Total scratch episodes (no.)

The scratch-related parameters for GENEActiv and Panoramic Bracelet will be derived by the ScratchPy algorithm.

##### **3.1.2.3. Wear Time Parameters**

- Number of available hours (h) or minutes (min)
- Number of hours (h) or minutes (min) of wear
- Number of wear hours (h) or minutes (min) while awake

The wear time parameters for GENEActiv and Panoramic Bracelet will be derived by the in-house built SKDH package.

### 3.1.3. Wearability and Comfort Questionnaire

At-home Panoramic Bracelet device wearability/comfort questionnaire responses from the at-home monitoring period will be summarized.

## 3.2. Secondary Endpoints

**Table 4. Secondary Objectives and Endpoints (Cohort A)**

Secondary Objective(s):	Secondary Endpoint(s):

 
• To assess the feasibility of recruiting pediatric participants to conduct a wearable device study.
 
	
 
• Recruitment data listed by age group:           
 
(a) Number of participants contacted
 
(b) Number of participants screened
 
(c) Number of participants enrolled over time
 
(d) Time taken (number of days) to enroll approximately 13 participants per group
 
 
 

 
• To assess the ability of pediatric participants to perform a battery of lab-based tasks.
 
	
 
• Total number of participants able to perform each of the 7 tasks
 
• Number of participants per age group able to perform each of the 7 tasks
 
• Percentage of tasks completed (from a total of 7 tasks)
 

 
• To assess the compliance in wearing the ActiGraph devices at home.
 
	
 
• Number of hours per day wearing the lumbar and wrist devices
 
• Number of days with more than 10 hours of wear time for lumbar device
 
• Number of days with more than 18 hours of wear time for wrist device
 

 
• To evaluate the participant's or caregiver's perception of wearability and comfort of ActiGraph and APDM devices during in-lab sessions.
 
	
 
• Wearability/Comfort Questionnaire for APDM device and for Actigraph lumbar and wrist device separately (All questions are on a 5-point Likert scale)
 
• Cognitive Debrief of Wearability/Comfort Questionnaire
 

 
To evaluate the participant's or caregiver's perception of wearability and comfort of ActiGraph devices during the at-home monitoring period.
 
	
 
Wearability/Comfort Questionnaire for Actigraph lumbar and wrist device separately (All questions are on a 5-point Likert scale)
 


 
To evaluate the effect of floor surface (carpet vs. tile) on gait metrics collected using ActiGraph and APDM devices.
 
	
Actigraph Lumbar and APDM:
 
 
Double support (sec)
 
Single limb support (sec)
 
Stance time (sec)
 
Swing time (sec)
 
Stride length (meters)
 
Step duration (sec)
 
Cadence (steps/min)
 
Gait speed (meters/sec)
 
Steps (steps)
 
Stride duration (sec)
 
 
The gait parameters for APDM will be derived from the manufacturer's algorithm^22. The gait parameters from the Actigraph sensor on the lumbar location will be derived by in-house built gaitPy algorithm^23.

**Table 5 Secondary Objectives and Endpoints (Cohort B)**

 
To assess the compliance in wearing the Panoramic Bracelet device at home.
 
	
Panoramic Bracelet (Days 1-7)
 
 
Number of available hours (h) or minutes (min)
 
Number of hours (h) or minutes (min) of wear
 
Number of wear hours (h) or minutes (min) while awake
 

 
To compare gait quality metrics collected using Panoramic Bracelet devices, APDM devices and GAITRite® walkway, during in-lab sessions.
 
	
 
GAITRite Walkway, APDM & Panaromic Bracelet devices 
 
Double support (sec)
 
Single limb support (sec)
 
Stance time (sec)
 
 
 

	
 
• Swing time (sec)
 
• Stride length (meters)
 
• Step duration (sec)
 
• Cadence (steps/min)
 
• Gait speed (meters/sec)
 
• Steps (steps)
 
• Stride duration (sec)
 
 
The gait parameters for GAITRite and APDM will be derived from their manufacturer's algorithms (GAITRite and/or PKMAS, APDM: Mobility Lab). The gait parameters from the Paronomic Bracelet devices will be derived by in-house built SKDH gait algorithm^27.

--	---

### 3.3. Exploratory Endpoints

**Table 6. Exploratory Objectives and Endpoints (Cohort A)**

 
• To investigate the feasibility of using a daily activity diary to provide context in pediatric physical activity data collected by ActiGraph devices at home in pediatric participants.
 
	
ActiGraph Physical Activity Endpoints from Wrist
 
 
• Light Activity Time (min)
 
• Moderate Activity Time (min)
 
• Vigorous Activity Time (min)
 
• Sedentary Activity Time (min)
 
• Non Sedentary Physical Activity (min)
 
• Moderate to Vigorous Physical Activity (MVPA, min)
 
• Calories (kcal)
 
• Total Activity Count for Axis X, Y, and Z
 
• Total Vector Magnitude
 
 
These parameters will be derived from the manufacturer's algorithms.
 
 
• Activity Diary 
 
1. Sickness or events preventing normal physical activity: Yes/No
 
2. Sport or very active physical activities: Yes/No
 
 
 

--	--

	
3. Length of time of sports or very active physical activities: <30 min, 30 min – 1 hr, > 1 hr

 
• To compare gait speed collected using the SIMI® system and GAITRite® walkway, during in-lab sessions.
 
	
 
• Gait speed measured by SIMI® system^28
 
• Gait speed measured by GAITRite® walkway derived during natural, slow and fast speed walk tasks
 

**Table 7 Exploratory Objectives and Endpoints (Cohort B)**

 
• To evaluate the participant's or caregiver's perception of wearability and comfort of Panoramic Bracelet device in-lab sessions.
 
	In-lab Wearability/Comfort Questionnaire for Panoramic Bracelet (wrist and lumbar) from Visit 1 (Day 1).

 
• To evaluate the effect of floor surface (carpet vs tile) on gait metrics collected using Panoramic Bracelet and APDM devices.
 
	
Panoramic Bracelet and APDM:
 
 
• Double support (sec)
 
• Single limb support (sec)
 
• Stance time (sec)
 
• Swing time (sec)
 
• Stride length (meters)
 
• Step duration (sec)
 
• Cadence (steps/min)
 
• Gait speed (meters/sec)
 
• Steps (steps)
 
• Stride duration (sec)
 
 
The gait parameters for APDM will be derived from the manufacturer's algorithm^22. The gait parameters from the Panoramic Bracelet devices will be derived by in-house built SKDH gait algorithm^27.

### 3.4. Other Endpoints

Participant demographics and other information will be recorded for each subject: age, sex, height, weight, race, ethnicity and handedness (using the Edinburgh Handedness Inventory (EHI)-short form).

### 3.5. Baseline Variables

Due to the nature of the study design, no baseline variables are defined.

Demographic variables (Section 3.4), floor type (carpet, tile), proximity of the device (Cohort B, Panoramic closer to wrist vs GENEActiv closer to wrist), and devices (GAITRite, APDM, Actigraph, GENEActiv, Panoramic Bracelet) may be adjusted as covariates in the statistical models.

### 3.6. Safety Endpoints

*An adverse event (AE) is defined as any untoward medical occurrence and can therefore be any unfavorable and unintended sign (including an abnormal laboratory finding), symptom, or disease, whether or not related to the participant's participation in the study.*

***Any AE that occurs from the time the participant consents to the clinical research through and including 12 hours after completion of the qualifying procedure will be recorded.***

## 4. ANALYSIS SETS (POPULATIONS FOR ANALYSIS)

Data for all participants will be assessed to determine if participants meet the criteria for inclusion in each analysis population prior to unblinding and releasing the database and classifications will be documented per standard operating procedures.

Population	Description
Full Analysis Set (FAS)	
All participants who have a signed and dated informed consent document, have assented to the study and are enrolled in the study.
 
Qualified male or female participants aged 3 to 17 years old inclusive. Qualified is defined as no significant health problems that would impair the completion of the physical activity tasks, does not carry any diagnosis of developmental delay and/or significant co-morbid medical conditions as determined by a medically qualified individual during medical history review with LAR and participant. Children who are ambulatory.

## 5. GENERAL METHODOLOGY AND CONVENTIONS

The primary analysis will be performed after database lock.

## 5.1. General Methods

Data will be summarized using descriptive statistics (number of subjects (n), mean, median, standard deviation (SD), minimum and maximum, as appropriate) for continuous (or near continuous) variables, and using frequency and percentages for discrete variables. The temporal data may be summarized over activity task during in-lab activities and over days for at-home monitoring.

### Cohort A:

The comparisons between devices (e.g. APDM vs Actigraph) will be investigated with Mixed Model Repeated Measures (MMRM), ANOVA or a non-parametric equivalent (Kruskal-Wallis, Friedman tests). Necessary covariates will be included such as demographic variables such as age and gender, and floor type. Pairwise comparisons will be performed with paired t-tests or their non-parametric equivalent (Wilcoxon Signed-rank test). If visual inspection of the data suggests that a transformation of the endpoints should be performed, this will be applied as appropriate prior to analysis and documented in the final report as required.

P-values will be generated where appropriate and any p-value  $< 0.05$  will be considered statistically significant. If multiple p-values are generated, an experiment wise significance threshold will also be provided for context using methods such as family wise error rate (FWER) and/or false discovery rate (FDR) control. P-values will be rounded to 3 decimal places and therefore presented as 0.xxx; P-values smaller than 0.001 will be reported as '<0.001'.

Agreement between two measurements will be assessed by the intra-class correlation coefficient (ICC, type 2 way random effects, absolute agreement), according to the following benchmarks:  $ICC \leq 0.4$  indicates 'poor', 0.4 to 0.59 'moderate', 0.6 to 0.74 'good', and 0.75 to 1 'excellent' agreement. In addition, Bland–Altman plots and 95% limits of agreement (average difference  $\pm$  1.96 standard deviation of the difference) will be used to visualize and quantify differences between endpoints derived from the reference devices and comparator device (Actigraph).

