parent(s)/LAR. The investigator must ensure that each participant and participant's parent(s)/LAR is fully informed about the nature and objectives of the trial and possible risks associated with participation. If the participant's parent(s)/LAR desires the participant to participate in the study and the participant wishes to participate in the study, an IRB-approved informed consent form will be signed and dated by the participant's parent(s)/LAR and a verbal or written assent from the participant will be collected (if applicable, as consistent with the participant's age and ability to provide assent), as required by the IRB. The informed consent and assent forms must be agreed by Pfizer and the IRB and must be in compliance with the International Council for Harmonisation (ICH) Good Clinical Practice (GCP), local regulatory requirements, and legal requirements.

The signed documents will be retained at the site, and the investigator or person designated by the investigator must document in the source documents that informed consent and assent were obtained.

The participant will be assigned a participant identifier after informed consent and assent are obtained.

Visit 1 (Day 1)

After informed consent and assent have been obtained, the following assessments will be performed during the study visit:

1. Collect participant demography and parent(s)/LAR's contact information.
2. Obtain medical and surgical history.
3. Review prior and concomitant treatments.
4. Confirm eligibility for the study based on inclusion/exclusion criteria.
5. Record height, leg length, and weight.
6. Handedness questionnaire: [Edinburgh Handedness Inventory \(EHI\)-short form \(Annex 4\)](#).
7. Place device under study and APDM devices on participant.
8. Walk on a GAITRite® walkway at participant's natural speed (3 rounds = ~20 feet x 3) and at varied speeds while wearing device under study and APDM system. Natural speed is participant's self-chosen pace and varied speeds includes participant's self-chosen slow pace ("Walk slow") for 3 rounds and fast pace ("Walk fast") for 3 rounds.
9. Walk on tile and carpet (3 rounds on each surface) at participant's natural speed while wearing device under study and APDM system.

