The proposed sample size for this study is approximately 39 participants in each cohort (approximately 13 in each age group). To the best of our knowledge, no relevant data has been published before to validate accelerometry-measured gait metrics against GAITRite® walkway or APDM in pediatric population. Using data from X9001198 study (healthy adult participants, ages 18-40 and 65-85 years), the Intraclass Correlation Coefficient (ICC) between gait speed obtained from the sensor data vs gait speed obtained from the reference comparator gait mat was 0.72 (when corrected for a systematic bias of 0.17 m/s). The ICC value for the null hypothesis is derived by using the median value of the lower bound of ICC for all gait metrics (8 spatial and temporal metrics). ICC_{null} was 0.27, range = [0, 0.66]. In order to reach ICC value of 0.72 with ICC_{null} value of 0.27 using a one-tailed test with alpha = 0.05 and power = 0.8 it is estimated that at least 17 participants will be needed. Therefore, approximately 20 adult participants (anticipating 15% attrition) are required for the validation analyses. Here, we double the amount to roughly 40 participants to account for potential higher variance in the healthy pediatric participants (ages 3 – 17). Since we have 3 age groups, each group will equally have 13 participants, which results in a total of 39 participants.

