### Cohort B:

The comparisons between devices (e.g. GENEActiv vs Panoramic Bracelet) will be investigated with mixed effect models. Necessary covariates will be included such as demographic variables such as age, gender, proximity of the device and floor type. Pairwise comparisons will also be performed with paired t-tests or their non-parametric equivalent (Wilcoxon Signed-rank test). Mean absolute percent error between the comparator and reference metrics will be computed and Bland-Altman plots and 95% limits of agreement will be used to assess the bias. The endpoints might be log transformed using  $\log(x+1)$ .

To assess the relationship of endpoints between devices, Deming regression will be used. Deming regression takes into account the variations from the multiple measures on both test devices and traditional methods. The slope and intercept from model fitting and their 95% CI

will be reported. The ratio of variances of the two devices will also be calculated. Weighted Deming and Passing-Bablok regression may also be used if deemed appropriate.

P-values will be generated where appropriate and any p-value < 0.05 will be considered statistically significant. If multiple p-values are generated, an experiment wise significance threshold might be provided for context using methods such as family wise error rate (FWER) and/or false discovery rate (FDR) control. P-values will be rounded to 3 decimal places and therefore presented as 0.xxx; P-values smaller than 0.001 will be reported as ‘<0.001’.

Agreement between two measurements will be assessed by the intra-class correlation coefficient (ICC, type 2 way random effects, absolute agreement), according to the same benchmarks used in Cohort A. The ICC will be computed and compared between each pair of endpoints, using mean/median/25% & 75% quantiles across daily records.

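### SAP 5.1 permits Kruskal-Wallis, and ANOVA not stated to be repeated-measures, for devices worn by the same child; the unit of the Cohort B paired tests is also not stated

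*SAP*

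**What the plan says.** **Cohort A.** SAP 5.1 says that device comparisons "will be investigated with Mixed Model Repeated Measures (MMRM), ANOVA or a non-parametric equivalent (Kruskal-Wallis, Friedman tests"). It gives no rule for choosing among the four and does not say that the ANOVA is repeated-measures. The follow-up tests are matched: "Pairwise comparisons will be performed with paired t-tests or their non-parametric equivalent (Wilcoxon Signed-rank test").

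The design is matched too. In the protocol (Visit 1, steps 8 to 10) the child walks "while wearing device under study and APDM system", and step 8 takes place on the GAITRite walkway. SAP Table 3 lists GAITRite, APDM and ActiGraph for the same walks. SAP 3.1.1 reduces each variable to one summary per activity.

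**Cohort B.** The overall method is different: "The comparisons between devices (e.g. GENEActiv vs Panoramic Bracelet) will be investigated with mixed effect models". It then adds: "Pairwise comparisons will also be performed with paired t-tests or their non-parametric equivalent (Wilcoxon Signed-rank test"). For the at-home endpoints, SAP 3.1.2 says "Each variable will be summarized daily or nightly, as appropriate". SAP 5.1 says the ICC is computed on summaries across daily records, but names no unit for the paired tests. Its general paragraph only allows, and does not require, summarising at-home data over days.

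In both cohorts "any p-value < 0.05 will be considered statistically significant". The protocol (Study Size) plans "approximately 39 participants in each cohort (approximately 13 in each age group").

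**The concern.** Kruskal-Wallis and one-way ANOVA compare separate groups of subjects. Applied to several devices on one child, they put the spread between children into the error term, although that spread is common to all devices and cancels in a matched analysis. In children aged 3 to 17 the spread in gait is likely to be large, so a real offset between devices can go undetected. Listing Kruskal-Wallis beside Friedman as interchangeable leaves an analyst with skewed data free to pick the wrong one, and an unmatched overall test could then precede matched follow-up tests.

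In Cohort B the risk runs the other way. About eight nights per child are not independent replicates. A paired test over all nightly pairs would understate the standard error of the mean difference and could contradict the mixed model of the differences in SAP 6.2.1.

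**Working it through.** **The plan's own figures.** The documents give no power or error rate for the tests in SAP 5.1; their only calculations are for the ICC (protocol, Study Size). With k = 2 measurements and t = ICC/(1 − ICC), the usual formula is n = 1 + 2k(z_α + z_β)² / [(k − 1)(ln C₀)²], C₀ = (1 + k·t₀)/(1 + k·t₁), one-sided α 0.05, power 0.80.
- Gait, 0.72 against 0.27: C₀ = 1.740/6.143 = 0.283, n = 16.5, so 17 as stated.
- Sleep, 0.88 against 0.36: C₀ = 2.125/15.667 = 0.136, n = 7.2, so 8 as stated.

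Both reproduce, and neither depends on the tests at issue.

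**Cohort A inputs.** n = 39 (protocol). Between-device correlation ρ = 0.72, which is the protocol's planning ICC: adult, bias-corrected, one sensor against the gait mat. Using it for every device pair is an assumption. Also assumed: normal data, equal SDs, two-sided 0.05, and the size of the shift.

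*Two devices.* The matched standard error of the mean difference is SD·√(2(1 − ρ)/n); the unmatched test uses SD·√(2/n). The unmatched statistic is therefore shrunk by √(1 − 0.72) = 0.529. Its critical value of 1.99 (76 df) acts like 1.99/0.529 = 3.76 on the correct scale, so null rejection is about 0.02%. Simulation gave 0.04% (ANOVA) and 0.01% (Kruskal-Wallis), against 5.3% for the paired t-test.

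Power at n = 39 for shifts chosen so that the paired t-test has 80% power:

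| ICC | shift (SD) | one-way ANOVA | Kruskal-Wallis |
|---|---|---|---|
| 0.50 | 0.46 | 53% | 50% |
| 0.72 | 0.34 | 20% | 20% |
| 0.88 | 0.23 | 0.7% | 1.1% |

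At ICC 0.72, shifts with 90% and 99% paired power leave Kruskal-Wallis 34% and 71%.

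*Three devices, one shifted by 0.3 SD (assumed), ICC 0.72.* The noncentrality for the matched F test is 39 × 0.3² × (2/3)/(1 − 0.72) = 8.36, which gives 72% power on 2 and 76 df. Simulated power:

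| Test | Power |
|---|---|
| Repeated-measures ANOVA | 73% |
| Friedman | 57% |
| Kruskal-Wallis | 6.9% |
| One-way ANOVA | 6.6% |

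With no shift, the two unmatched tests reject near 0% and the two matched tests about 5%.

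*A large bias.* The only device bias in the documents is 0.17 m/s in gait speed (adult data). The SD is not given, so a range is assumed; ICC 0.72, two devices, n = 39:

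| SD (m/s) | paired t | Kruskal-Wallis |
|---|---|---|
| 0.15 | 100% | 100% |
| 0.20 | 100% | 99.8% |
| 0.25 | 100% | 95% |
| 0.30 | 99.6% | 79% |
| 0.40 | 93% | 41% |

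**Cohort B.** 39 children × about 8 nights (days 8 to 15, SAP 6.2.1) = 312 pairs. Let ρ_d be the within-child correlation of the nightly device differences, which the documents do not give. If nights are pooled, the variance of the mean is understated by 1 + 7ρ_d, and the true type I error is about 2[1 − Φ(1.96/√(1 + 7ρ_d))].

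| ρ_d (assumed) | 1 + 7ρ_d | formula | simulated |
|---|---|---|---|
| 0 | 1.00 | 5.0% | 4.6% |
| 0.05 | 1.35 | 9.2% | 9.1% |
| 0.1 | 1.70 | 13.3% | 13.4% |
| 0.2 | 2.40 | 20.6% | 20.3% |
| 0.3 | 3.10 | 26.6% | 26.3% |
| 0.5 | 4.50 | 35.6% | 35.3% |

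The Wilcoxon test behaves about the same. One mean difference per child gives 4.6% to 5.3%.

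**The case against.** SAP 5.1 is a general menu, and the same sentence offers MMRM and Friedman, which are sound. The next sentence calls for covariates, which Kruskal-Wallis cannot carry. The objective-level sections 6.1, 6.3.6 and 6.5.2 each specify a mixed model with subject as random effect, and 6.4.2 and 6.6.2 carry those plans to the Cohort B in-lab data. Section 6 names neither Kruskal-Wallis nor ANOVA. The word ANOVA could be meant as repeated-measures. All of this stands, and it makes the fault a permitted option only. It does not make Kruskal-Wallis a valid option for matched data.

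Three stronger readings are tempting, and the documents do not support them.
- **That nearly all power is lost.** This is so for small shifts at high correlation. It is not so in general: at 0.17 m/s with an SD up to 0.25 m/s, little is lost.
- **That a non-significant device test would be read as agreement.** The SAP judges agreement by absolute-agreement ICC, Bland-Altman limits and percent error, none of which uses these tests.
- **That the Cohort B paired tests reject too often as planned.** A paired test keeps the device pairing within the child. Only the clustering of nights could be missed, and only if nights are pooled, which no section says. SAP 6.2.1 lists no paired test, models nightly differences with a random subject effect, and computes accuracy by day. The paired-test sentence also serves in-lab data, where there is one summary per activity and the test is valid.

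On Cohort B, what remains is that the tests are announced as planned and their unit is left open. A positive ρ_d is plausible, since device position on the wrist is fixed by child and 6.2.1 itself allows a subject effect on the difference.

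**Conclusion.** The point holds as a wrongly named option in SAP 5.1. Kruskal-Wallis, and ANOVA if read as one-way, are the wrong class of test for devices worn together. In the three-device case they have about 7% power where matched tests have 57% to 73%, and they reject near 0% under the null. Those figures rest on n = 39, ICC 0.72 for every device pair and an assumed 0.3 SD shift; the loss shrinks with larger bias or lower correlation. The main inference, the agreement statistics and the sample size are unaffected.

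The Cohort B part is a missing specification. The 9% to 35% type I error applies only if nights are pooled and the assumed ρ_d lies between 0.05 and 0.5; at ρ_d = 0, or with one value per child, the test holds about 5%.

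**What to change.** - SAP 5.1, Cohort A: delete Kruskal-Wallis, write repeated-measures ANOVA in place of ANOVA, and keep MMRM and Friedman with the paired t-test or signed-rank test as follow-up.
- SAP 5.1, Cohort B: state that at-home paired tests use one mean difference per child, or are run separately for each day, and that the mixed model of the differences in 6.2.1 is the main inference.

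The cost is about two sentences. No data collection, sample size or endpoint changes.
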